# EIRB Protocol Template (Version 1.3)

## 1.0 General Information

**\*Please enter the full title of your study:**

Assessing the Impact of Post-Exercise Photobiomodulation Application on Performance, Recovery, and Behavioral State in a Trained Special Operator Population

**\*Please enter the Protocol Number you would like to use to reference the protocol:**

Photomedicine Project 14: PBMT for Performance Enhancement in SOF

\* This field allows you to enter an abbreviated version of the Protocol Title to quickly identify this protocol.

**Is this a multi-site study (i.e. Each site has their own Principal Investigator)?**

No

**Does this protocol involve the use of animals?**

Yes  No

**3.4 If applicable, please select the Designated Site Approval(s):**

Add the name of the individual authorized to approve and sign off on this protocol from your Site (e.g. the Site Chair).

**4.0**  
**Project Information**

**4.1 \* What department(s) will be associated with this protocol?** Other**4.2 \* Is the IRB of record for this study an IRB/HRPP that does NOT use EIRB? If Yes, complete the application according to the IRB/HRPP Determination.**

If your Projects or Protocols are under the oversight of another IRB that does use EIRB, stop this submission and contact the core site and request an invitation as a performing site.

If your Project or Protocol is now being submitted for the first time to an IRB that does use EIRB, continue with this application and answer the questions to be reviewed by the IRB.

Answering yes means the board of record is an IRB that does NOT use EIRB.

Yes  No

**4.3 \* Is this protocol research, expanded access, or humanitarian use device?**

Yes  No

**4.4 \* What type of protocol is this?**

- Behavioral Research
- Biomedical Research
- Clinical trial (FDA regulated)
- Educational Research
- Expanded Access
- Humanitarian Use Device (HUD)
- Psychosocial Research
- Oral History
- Other

**4.5 Are you conducting this project in pursuit of a personal degree?**

Yes  No

**4.7 \* Is this human subjects research? (As defined by 32 CFR 219) Human subject means a living individual about whom an investigator (whether professional or student) conducting research:**

(i) Obtains information or biospecimens through intervention or interaction with the individual, and uses, studies, or analyzes the information or biospecimens; or  
(ii) Obtains, uses, studies, analyzes or generates identifiable private information or identifiable biospecimens.

Yes  No

**4.8 \* Do you believe this human subjects research is exempt from IRB review?**

Yes  No

## Personnel Details

### 5.1 Does the Principal Investigator have a Permanent Change of Station (PCS) Date or Estimated Institutional Departure Date (EIDD)?

Yes  No

### 5.2 List any Research Team members without EIRB access that are not previously entered in the protocol:

No records have been added

#### 5.4

#### Will you have a Research Monitor for this study?

- Yes
- No
- N/A

#### 6.0

#### Data/Specimens

#### 6.1 Does the study involve the use of existing data or specimens only (no interaction with human subjects)?

- Yes
- No

#### 7.0

#### Funding and Disclosures

#### 7.1 Source of Funding:

Funding Source	Funding Type	Amount
:   USUHS Award Number 	:    	250000

Total amount of funding:

250000

#### 7.2 Do you or any other Investigator(s) have a disclosure of a personal interest or financial nature significant with sponsor(s), product(s), instrument(s) and/or company(ies) involved in this study?

- Yes
- No

All personnel engaged in research must complete and attach a Conflict of Interest (COI) form.

## 8.0 Study Locations

### 8.1 Is this a collaborative or multi-site study? (e.g., are there any other institutions involved?)

Yes  No

### 8.3 Are there international sites?

Attach international approval documents, if applicable, when prompted. Note: Ensure local research context has been considered

Yes  No

### 8.4 Is this an OCONUS (Outside Continental United States) study?

Yes  No

Select the area of responsibility:

Have you obtained permission from that area of responsibility? (This is a requirement prior to study approval)

Yes  No

## 9.0

### Study Details

#### 9.1 Key Words:

Provide up to 5 key words that identify the broad topic(s) of your study

Photobiomodulation, Photomedicine, Performance Enhancement, Quadriceps, Special Operations

## 9.2 Background and Significance:

Include a literature review that describes in detail the rationale for conducting the study. Include descriptions of any preliminary studies and findings that led to the development of the protocol. The background section should clearly support the choice of study variables and explain the basis for the research questions and/or study hypotheses. This section establishes the relevance of the study and explains the applicability of its findings

Military demands require for Special Operations Forces (SOF) populations to be physically fit, ready for deployment at any time. To meet this requirement, Special Operators ("Operators") train regularly to reach peak performance. This training can be taxing on one's body, as it is nearly always recovering. To provide elite performance and recovery coaching, the United States Special Operations Command (SOCOM) initiated Tactical Human Optimization Rapid Rehabilitation and Reconditioning (THOR3), in 2009: a program for Special Forces to provide wholistic wellness and health to Operators through mental, physical, nutrition, spiritual, and cognitive programming. Ultimately, the goal of THOR3 is to optimize physical and mental health performance, consequently increasing operational longevity and warfighter readiness. THOR3 focuses on providing evidence-based interventions, tracks data of Operators' performance, and is on the cutting-edge of performance enhancement in the DoD with elite trainers and providers. Thus, this program is at the tip-of-the-spear for initiatives to increase strength, conditioning, and recovery (Wyatt, 2017).

A pioneering performance and recovery enhancement tool is Photobiomodulation therapy (PBMT). PBMT is a noninvasive treatment where a device that emits low level lasers is applied to a body area to enhance recovery and improve performance (Dompe, 2020). Studies in athletes have shown performance (improved maximum voluntary contraction, sprint time, CMJ height, fatigue index, time on pitch, VO2max, volume and time to anaerobic and aerobic threshold appearance) and recovery (decreased inflammatory and oxidative stress markers, delayed onset muscle soreness) benefit with both pre-and post-workout application of PBMT (Ailioaie, 2021).

When applied to the lower body pre-exercise, PBMT has been found to prevent increase of /decrease creatine kinase (CK) activity, a biomarker of muscle damage. This reduction, as compared to placebo, has been observed after cycling tests (Junior, 2009; Junior, 2011), eccentric exercise (Baroni, 2010; Vanin, 2016; De Paiva, 2016; Antonielli, 2014; de Oliveria, 2017), and running tests (Tomazoni, 2019). A case-control study with identical twins participating in a workout regimen also showed that PBMT application post-exercise reduced creatine kinase (CK) (Ferraresi, 2016). Transferring this observation to other activities, PBMT has also shown to decrease/prevent increase of CK in sports performance such as volleyball, (Ferraresi, 2015) and futsal (De Marchi, 2019). Compared to other modalities, namely, cold-water immersion (Junior, 2011), or cryotherapy (De Paiva, 2016), PBMT was significantly more effective in positively altering CK activity. Similarly, pre-application of PBMT has also shown to reduce lactate after sprint/running tests (Pinto, 2016; Tomazoni, 2019), eccentric exercise (Baroni, 2010; de Oliveria, 2017) futsal matches (De Marchi, 2019), and cycling tests, in which it also more effectively reduced lactate as compared to other modalities (Junior, 2011). Alike results have been noted for Interleukin-6 (IL-6) (Vanin, 2016; de Oliveria, 2017; Tomazoni, 2019), and carbonylated proteins indicative of an oxidative stress environment (De Marchi, 2019; Tomazoni, 2019; Ferraresi, 2016). Taken together, these results suggest that PBMT is protective against muscle damage.

Performance metrics have also shown improvement with PBMT. Maximum voluntary contraction (MVC) has been found to increase/decrease to a lesser extent after an eccentric exercise routine when PBMT was applied pre-workout, as compared to placebo (Baroni, 2010; Antonielli, 2014, Vanin, 2016). Maximum involuntary contraction (MVIC) also increased with application of PBMT prior to an eccentric exercise program (de Oliveria, 2017; De Paiva, 2016). PBMT application can also increase the number of maximum repetitions (de Brito, 2014), torque (De Carvalho, 2020; Baroni, 2015; Dornelles, 2019), and CMJ performance (Dornelles, 2019). Succinctly, Rossato et al. (2020) found that application of PBMT decreases fatigue while maintaining or increasing performance, thus enabling athletes to output the same total work with the availability to complete additional sets. Pre-application of PBMT prior to a futsal match also significantly increased the time players were able to stay on the pitch (De Marchi, 2019). Thus, PBMT is effective at increasing performance metrics across a variety of outcomes.

Self-reported behavioral effects related to physical performance also show positive effects from PBMT. PBMT application has been found to reduce self-reported delayed-onset muscle soreness (DOMS) and self-reported fatigue. A randomized, double-blinded, placebo-controlled clinical trial found that PBMT decreased DOMS as compared to placebo and cryotherapy alone, or the

combination of cryotherapy and PBMT (De Paiva, 2016). Other similar studies found a significant difference in decreased DOMS as compared to placebo (Antonialli, 2014; de Oliveria, 2017; Ferraresi, 2016). During sprint tests, in a randomized, crossover, double-blind, placebo-controlled clinical trial conducted with rugby players, PBMT decreased self-perceived fatigue post sprint test (Pinto, 2016). PBMT is effective in reducing perception of fatigue and soreness, even when compared to an equivalent placebo.

Outside of self-reported fatigue or DOMS, there is less information on the potential behavioral effects of PBMT focal application (e.g., quadriceps). Studies, however, have shown that transcranial application of PBMT has a role in recovery of brain injury and disorders (e.g., traumatic brain injury, Parkinson's disease, and Alzheimer's), psychological disorders (e.g., anxiety and depression), and cognitive enhancement in both healthy and cognitive declining populations (Hamblin, 2016).

Taken as a whole, PBMT is a promising avenue for increasing overall performance by enhancing recovery processes, self-reported DOMS and fatigue, and potentially positively affecting behavioral health in the Special Operator population. We will conduct a single-blinded randomized-control trial with sham control to investigate the effectiveness of providing PBMT post physical training in a SOF population, thus translating this cutting-edge research to application in the THOR3 setting.

### 9.3

#### **Objectives/Specific Aims/Research Questions:**

Describe the purpose and objective(s) of the study, specific aims, and/or research questions /hypotheses

Aim 1: Describe physiologic effects of PBM application post-exercise in SOF operators undergoing THOR3 coach led training

Aim 2: Describe behavioral effects of PBM application post-exercise in SOF operators undergoing a THOR3 coach led training

### 9.4 Study Design:

Describe study design in one to two sentences (e.g., prospective, use of existing records/data /specimens, observational, cross-sectional, interventional, randomized, placebo-controlled, cohort, etc.). Specify the phase – Phase I, II, III, or IV – for FDA-regulated investigational drug research

Randomized, single-blind, sham control trial

### 9.5 Target Population:

Describe the population to whom the study findings will be generalized

Active-Duty Service Members, combat/tactical Athletes such as police officers and firefighters, collegiate athlete populations

### 9.6 Benefit to the DoD:

State how this study will impact or be of benefit to the Department of Defense

Military demands require for SOF populations to be physically fit, ready for deployment at any time. SOF are responsible for executing specific missions and objectives that may be outside of the capacity of conventional forces, thus filling a necessary void in the nation's defense. Increasing performance and/or recovery of these Special Operators will contribute to their individual warfighter readiness and collectively positively influencing operational longevity.

## 10.0

## Study Procedures, Data Management, and Privacy

### 10.1 Study Procedures:

Describe step-by-step how the study will be conducted from beginning to end

Study activities will occur at Joint Base Lewis-McChord (JBLM) within the 1st Special Forces Group (SFG). Study activities, including recruitment, will occur in the THOR3 Clinic area or other applicable 1st SFG areas.

#### **Recruitment, Pre-Screening (before consent), Study Introduction & Informed Consent:** Potential participants will be identified via three methods:

1. Participants may self-refer to participate in the study if they become aware of the study by study flyer (Appendix P) or word of mouth. Interested potential participants will be able to contact a member of the study team via phone or email.
2. Mass briefs at THOR3 coach-lead trainings.
  - Briefings will occur at regular intervals, about every 3 weeks, for each training class at the 3 Operator focused training sessions. In the course of a month, there will be about 4 briefings.
  - Briefings will take no more than five (5) minutes. The briefs will be scheduled to occur prior to the coach led session. Consenting procedures will not occur during these informational briefs.
  - Leadership would only include the OIC of THOR3, not Group Leadership. Every effort will be made to ensure there is not undue coercion.
  - "Thank you for taking a few minutes to listen to this brief. We are conducting a research study to assess utilizing light therapy to increase recovery post training. There is the possibility that it can decrease inflammation, soreness, and fatigue and thus increase performance. We will ask you to complete a baseline visit, where we collect some self-reported demographic and health information, and measure your height, weight, and body fat. We will also ask you to complete a strength test and a counter movement jump. We will assign you an Oura Ring to wear for the duration of the study. This visit will take about 45 minutes. Then for 3 weeks, we will ask to provide light therapy 3 times a week after THOR3 coach led training. You will be randomly assigned to an active treatment or sham treatment group. Each group will wear headphones and blackout glasses. These sessions should take 20 minutes. Each week we will ask you to complete a countermovement jump, and fill out some questionnaires. These visits will take about 15 minutes. We will also ask you to fill out a daily pain questionnaire, and complete an activity log, which will take about 5 minutes. At the end of the three weeks, we will test your strength and counter movement jump again and ask you to fill out final questionnaires. This will take about 25 minutes. You will be compensated at each weekly visit, for a total of 150 USD. If you are interested in participating or in learning more about the study, please see a member of the research study team."
3. Study advertisements (Appendix P) will be posted in THOR3 and 1st SFG areas that operators frequent.

If a potential participant expresses interest in learning more about the research study, a member of the research staff will briefly introduce the study, express the voluntary nature of participation, assess interest in participating, and screen the potential participant for eligibility. Eligibility will be determined in person (individually, with a study team member) using the Inclusion/Exclusion Case Report Form (CRF) (Appendix A). Additionally, the potential participant may be provided with a study flyer.

Pre-screening conversations may also take place over the phone, should a participant contact the study team, using the Screening Script (Appendix M). Potential participants who meet initial eligibility per the Screening Script and express interest in participating will be asked to come to the THOR3 area to confirm final eligibility with an authorized study team member.

If the potential participant meets eligibility criteria and expresses interest in participating, an authorized study team member will assess whether the individual is comfortable with a group consent or an individual consent discussion. In accordance with the individual's preference, the authorized study team member will initiate the formal consent discussion and, if applicable, obtain informed consent (as outlined in Protocol Section 13.4).

If a potential participant would like additional time to review the consent form, study procedures, risks and benefits, etc. they will be provided with a consent form to take home and, if applicable, they may return at a later date to have any and all remaining questions answered and to finish the consent process.

The research team will keep a password-protected electronic Screening Log (Appendix N), containing initials, date of birth (DOB) and eligibility/ineligibility status, in a secure folder on a secure drive, accessible only by authorized users. This log is needed to avoid any duplicative screening of individuals. This log, therefore, will include initials and dates of birth (DOB) for those that screened formally and informally. Screening IDs will be different from study IDs that are assigned post-consent.

Participants that consent to participate will be added to a Master List (Appendix O) that will match the participants unique study ID with their name and other direct identifiers. The Master List will be stored in a password-protected electronic document on a common access card (CAC)-enabled server; only on-site study team members will have access to this file. This coded study ID will be used on all research data collection forms in place of the participant's name, Department of Defense (DoD) ID, or other protected identifier.

#### **Contact Information Data Collection (post-consent):**

Immediately following consent, the participant will complete an Intake CRF (Appendix B). The Intake CRF will collect participant contact information (full name, preferred phone number, email address, etc.).

With the exception of the Consent Form, the Intake CRF is the only paper research form that will contain participant identifying information. The Intake CRF will be kept with the signed consent forms (in a locked cabinet inside of a locked room) and stored separately from all other paper research forms.

#### **Demographics, & Baseline Data Collection:**

Prior to receiving study treatment, participants will complete a Demographics CRF (Appendix C) which collects relevant demographics including: personal demography, military and employment demography, and study-specific demography.

Additionally, participants will complete a Baseline Data Collection CRF (Appendix D) that collects: relevant medical history, military & work status, validated self-report measures, and study-specific measures. The following study-specific measures will be collected by a study team member:

- Fitzpatrick Skin Phototype
- Height, weight, and body fat composition (measured by bioelectrical impedance with InBody 770)
- Measurements of the participant's quadriceps to calculate the appropriate PBMT dose. (See Appendix S for PBM dosing information).
- Assessments of both legs:
  - CMJ, assessing jump height, time to take-off, RSImod, Eccentric Deceleration Impulse, Countermovement Depth, Concentric Impulse, Movement Start to Peak Power, and any asymmetries, and
  - Isometric and isokinetic dynamometer testing, assessing isolated strength in the lower body (i.e., unilateral Peak Torque and Rate of Force Development of quadriceps and hamstrings).
  - Processes for these tests can be found in the Appendices L and W. CMJ data will be output from the Force Decks software and recorded directly by the study team to the Appendix D and E CRF tables at each test iteration.

Each participant will be assigned an Oura Ring at baseline. Participants will be instructed to wear the Oura Ring for the duration of the study. The Oura Ring will continuously measure sleep quality, heart rate, blood oxygen saturation percentage (SpO2) levels, and activity. Oura Ring data will be securely stored in OuraTeams with access only for research team members.

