#### Photobiomodulation Treatment (PBMT)

PBMT will be delivered at 40W. A member of the study team will use the quadriceps measurements of the treatment area to calculate the PBMT treatment time (approximately 5-20 minutes). PBMT treatment will be provided up to 3 times a week, for 3 weeks. Participants will be asked to engage in 3 sessions per week; however, due to operational demands, we understand that they may not be able to attend all sessions and will then aim to minimally have them attend 2 sessions per week.

PBMT will be provided by a trained study team member. Training for the PBMT will be conducted by a LightForce representative. PBMT will be delivered using the LightForce® XLi 40W device with the Smart Hand Piece technology, created by LiteCure, LLC/DJO (New Castle, DE) which has a built-in accelerometer in the hand piece that controls the speed of light delivery to the treatment area. The LightForce® XLi therapy laser is an FDA cleared device for the treatment of pain. The trained team members will use the Smart Hand Piece technology, which achieves effective treatments and improves dosing accuracy by assessing the operator's speed and providing real-time visual (red – amber – green light) and sensory feedback. The Smart Hand Piece is calibrated to shut-off when moving too slowly, and warn the operator when moving too fast by vibrating. (See LightForce Brochure). The therapy is delivered through a flexible optical fiber threaded through the hand piece, which contains a rolling glass massage ball. PBMT will be delivered at specified J/cm^2 and applied to the quadriceps area.

In order to facilitate participant blinding to their randomized study group, all participants (regardless of their assigned study group) will be asked to wear blackout glasses and headphones during their treatment.

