#### **Follow-Up Data Collection:**

Follow-up data will be recorded on Appendix E Follow-up Data Collection CRF.

Regardless of study arm assignment, all participants will be asked to log their daily activity and pain (Appendix F Activity Log CRF) and wear the Oura Ring for 3 weeks.

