## 11.0 Statistical/Data Analysis Plan

### 11.1 Statistical Considerations:

List the statistical methods to be used to address the primary and secondary objectives, specific aims, and/or research hypotheses. Explain how missing data and outliers will be handled in the analysis. The analysis plan should be consistent with the study objectives. Include any subgroup analyses (e.g., gender or age group). Specify statistical methods and variables for each analysis. Describe how confounding variables will be controlled in the data analysis

Descriptive statistics will report location and scale in terms of mean and standard deviation for normally distributed variables, median and interquartile intervals for ordinal metric variables, and in terms of proportion and size for categorical variables. Descriptive statistics will be reported for baseline demographic and clinical characteristics at an overall level and by initial treatment group.

Outliers will be removed if determined to be erroneous based on relevant clinical expertise. Confounding will be principally controlled by randomization. In regards to the treatment of missing data, Oura Ring data will be analyzed despite presence of missing data at any point; with regards to non-continuous outcomes, data will be analyzed only if baseline and the 3-week follow-up are both present. In the event of missing data for a mid-point follow up (i.e., not baseline or the 3-week follow up), said patient will still be included in all models.

Statistical analyses will use generalized additive models predicting the change in outcome measures at 3 weeks relative to baseline for all measures except Oura Ring data. Oura Ring data will be aggregated by averaging readings across each 24-hour period and will be modeled using multi-level models incorporating random effects. Sensitivity analyses will be performed on longitudinal data for each outcome metric and will include multi-level models incorporating random effects as well as control variables to account for any differences explained by a selection of patient characteristics (such as body weight, etc.).

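### The Oura Ring analysis names no pre-treatment window, baseline term or treatment contrast; specifying all three is a cheap gain in precision

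*Combined protocol and SAP*

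**What the plan says.** **Ring wear.** Section 10.1, under demographics and baseline data collection, states "Each participant will be assigned an Oura Ring at baseline" and "Participants will be instructed to wear the Oura Ring for the duration of the study". That section describes a visit that precedes study treatment. The recruitment brief in 10.1 has the same order: ring at the baseline visit, then 3 weeks of light therapy. Under follow-up data collection, participants are asked to "wear the Oura Ring for 3 weeks". Treatment has the same length: "PBMT treatment will be provided up to 3 times a week, for 3 weeks". No minimum gap between ring issue and the first session is given. The ring is not among the items listed for the baseline form (Appendix D) in section 10.2.

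**Analysis.** Section 11.1 uses models "predicting the change in outcome measures at 3 weeks relative to baseline for all measures except Oura Ring data". For the ring, "Oura Ring data will be aggregated by averaging readings across each 24-hour period and will be modeled using multi-level models incorporating random effects". Section 11.6 repeats this. On missing data, "Oura Ring data will be analyzed despite presence of missing data at any point", so no pre-treatment reading is required. Sensitivity models add patient characteristics, with body weight as the example; an earlier ring value is not named.

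**The concern.** The other outcomes are each set against the participant's own starting value. The ring outcomes are exempted from that approach, and nothing is put in its place. Sleep and heart rate are likely to differ between people more persistently than they vary within a person from week to week. If so, an arm comparison that does not adjust for starting level is dominated by who happened to be allocated where. Randomisation protects against bias but not against that noise.

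The ring is the trial's only objective source on sleep and continuous heart rate. With 42 to 43 analysed per arm, and section 11.5 accepting that power may be inadequate, readings that could sharpen the comparison should not be left without a planned use.

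**Working it through.** **The plan's own figure.** Section 11.5 gives 80% power at 85 analysed and 90% at 108, with effect size 0.15 and a 5% level. Reading 0.15 as f², an overall F test in linear regression with four predictors gives 80.3% and 90.1%, so the figures reproduce. The number of predictors is inferred, since the plan does not state it. This calculation is generic and does not bear on the ring outcomes.

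**Inputs for the ring.** From the documents: 3 weeks of treatment (21 days) and 42 to 43 per arm (42.5 used). Assumed, because the documents give no standard deviation or correlation: daily variance 1, intraclass correlation ρ of 0.3, 0.5 or 0.7, compound symmetry, 21 complete days, and an arm difference in mean level as the contrast.

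**Step 1. Variance without a baseline.** The variance of one person's 21-day mean is ρ + (1 − ρ)/21.

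- ρ = 0.3: 0.3 + 0.7/21 = 0.333; between-person share 0.3/0.333 = 90%
- ρ = 0.5: 0.5 + 0.5/21 = 0.524; share 95%
- ρ = 0.7: 0.7 + 0.3/21 = 0.714; share 98%

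A random intercept estimates this between-person component. It does not take it out of the standard error of an arm difference in level.

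**Step 2. Adding the mean of k pre-treatment nights as a covariate.** The share of variance removed is r² = ρ² / {[ρ + (1 − ρ)/k] × [ρ + (1 − ρ)/21]}.

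| ρ | k = 2 | k = 3 | Equivalent sample size at k = 3, 1/(1 − r²) |
|---|---|---|---|
| 0.3 | 0.09/(0.650 × 0.333) = 42% | 0.09/(0.533 × 0.333) = 51% | 2.0 times |
| 0.5 | 0.25/(0.750 × 0.524) = 64% | 0.25/(0.667 × 0.524) = 72% | 3.5 times |
| 0.7 | 0.49/(0.850 × 0.714) = 81% | 0.49/(0.800 × 0.714) = 86% | 7.0 times |

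One night alone would remove 27%, 48% or 69%.

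**Step 3. Detectable difference at 80% power.** This is (1.96 + 0.84) × √(2 × variance/42.5), in daily standard deviations. With 3 baseline nights it falls from 0.35 to 0.25 (ρ = 0.3), from 0.44 to 0.23 (ρ = 0.5) and from 0.51 to 0.19 (ρ = 0.7).

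**Step 4. Stress test.** If within-person deviations have a day-to-day autocorrelation of 0.5 instead of being independent, 3 nights remove 36%, 58% or 77%. Slow drift over the 3 weeks would also reduce the gain; that was not quantified.

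**The case against.** A reader might infer that the ring is worn only during treatment, so that no baseline can exist. The documents do not support that. The ring is handed out at a pre-treatment visit for the whole study, and the 3-week statement sits under follow-up, where it may describe follow-up wear only. Some pre-treatment readings may well exist; how many is not stated. Appendix K, the data collection schedule, is not in the text available for this review and may settle the timing.

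A reader might also infer that the plan rules out a baseline value and that the comparison must carry the full between-person variance. The plan is silent rather than exclusive. A multi-level model of daily data could use pre-treatment days as responses, and under a treatment-by-day contrast the random intercept cancels, so differences in level drop out. Both points stand, and the size given here is therefore conditional on a mean-level contrast. They do not remove the gap, because no contrast is named. A slope contrast without pre-treatment days would also absorb into the intercept any effect present from the first session.

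Nor is the ring the only objective measure of recovery: jump testing and dynamometry are objective too. Finally, the aims in section 9.3 are descriptive, section 11.5 describes a pilot, and no ring outcome is named as primary. That limits the importance of the point but does not argue against a low-cost gain.

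**Conclusion.** The point holds as a gap in specification with a likely cost in precision. Sections 11.1 and 11.6 exempt the ring outcomes from the change-from-baseline models and name no pre-treatment window, baseline term or contrast. Section 10.1 leaves the start of wear unclear. For an arm difference in mean level, about 3 pre-treatment nights as a covariate would remove roughly half to six-sevenths of the variance over the assumed range of correlations, and 2 nights roughly two-fifths to four-fifths.

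These sizes rest on assumed correlations, compound symmetry and complete 21-day data, and they shrink under autocorrelation, drift or missing days. The randomised comparison remains unbiased throughout. This is a cheap improvement.

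**What to change.** 1. Reconcile the two wear statements in section 10.1, so that wear starts when the ring is issued at the baseline visit (or at consent) and runs to the final visit.
2. Label all ring readings before the first session as baseline. Aim for about 3 nights where the existing schedule allows, use whatever nights exist otherwise, and do not delay treatment to obtain them. State on which side the day of the first session falls, since readings are averaged over 24 hours.
3. In sections 11.1 and 11.6, prespecify the arm difference over on-treatment days as the ring contrast, and enter each person's baseline mean as a covariate in the multi-level model.
4. State a rule for participants with few or no baseline nights, so that they stay in the analysis.

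The cost is a scheduling sentence, one model term, the missing-baseline rule and a few extra days of use per ring. The documents do not give the interval between the baseline visit and the first session, so the number of nights achievable is unknown and some participants may contribute none.
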